Xbox Kinect™ to Promote Physical Fitness and Lean Mass in Severely Burned Children: A Randomized Controlled Trial

4-4-2020

Study Protocol

Background: Burns lead to persistent and detrimental muscle breakdown and weakness and poor physical fitness so Rehabilitation following burns is integral to improving physical and psychological outcomes. This study was undertaken to evaluate an alternative exercise rehabilitation strategy, so the aim of this work involving To explore the outcomes of an Xbox Kinect intervention on muscle strength, lean body mass (LBM) and cardiopulmonary fitness in severe pediatric burn.

Methods: Forty burned children with burns covering 40–60% of the total body surface area (TBSA), aged 10–16 years, were randomized into the standard of care (n=20), and Xbox training group (n=20) groups. All burned children received 12 weeks of routine physical therapy program (RPTP). In addition, the Xbox group received Xbox training involving five games for 50min a day, three times a week for 12 weeks .Outcomes were leg muscle strength was assessed as peak torque using a Biodex Isokinetic Dynamometer, Oxygen consumption capacity, measured as peak VO₂, was studied using a modified Bruce treadmill protocol, and lean body mass was determined using dual-energy X-ray absorptiometry. Outcomes were measured at baseline and after 12 weeks of intervention.

Conclusion: These findings suggest that the use of XbK intervention is a valuable, feasible and pleasant approach in order to improve muscle strength, lean body mass (LBM) and cardiopulmonary fitness in severe pediatric burn Xbox Kinect virtual reality could offer as a therapeutic and motivational tool when used with children burn.

Keywords: Severely burned children, interactive video games, Xbox Kinect™ ; lean body mass; VO₂ Peak; muscle strength; Enjoyment.

Statistical Analysis Plan

Reported data was analyzed using Statistical Package for Social Sciences (SPSS) computer program (version 23 windows) (Charles R Flint, New York, USA). Normality test of data using Shapiro-Wilk test was used, that reflect the data was normally distributed. There were no univariate or multivariate outliers, as assessed by boxplot and Mahalanobis distance ($p > 0.05$), respectively; there were linear relationships, as assessed by scatterplot; no multicollinearity. There was homogeneity of variances ($p > 0.05$), as assessed by Levene's test of homogeneity of variances. So, parametric analysis was performed.

Potential differences in baseline demographic between groups were examined using independent sample t-tests. 2x2 mixed design MANOVA was used to examine the effect of

treatment on the measured dependent variables (LBM, trunk, leg, Vo2 and PT) within group as the between-subject variable (experimental received and control received), and time as the within-subject variable (pre and post treatment). The variable of interest was the group-by- time interaction at an a priori alpha level of 0.05 and 95 % confidence interval.

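### Does the plan misdescribe its comparison by not saying, in the aim and Conclusion, that Xbox training was added to routine therapy?

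*Combined protocol and SAP*

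**What the plan says.** The whole Study Protocol is about the length of an abstract. Its Background gives the purpose and the aim in one sentence: "to evaluate an alternative exercise rehabilitation strategy, so the aim of this work involving To explore the outcomes of an Xbox Kinect intervention". The outcomes named are muscle strength, lean body mass and cardiopulmonary fitness.

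The Methods follow directly. Forty children "were randomized into the standard of care (n=20), and Xbox training group (n=20) groups". The routine programme goes to both arms: "All burned children received 12 weeks of routine physical therapy program (RPTP". The experimental component is then described: "In addition, the Xbox group received Xbox training involving five games for 50min a day, three times a week for 12 weeks".

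The Conclusion reads: "These findings suggest that the use of XbK intervention is a valuable, feasible and pleasant approach in order to improve muscle strength". It goes on to name lean body mass and fitness, and to suggest that Xbox virtual reality may have a therapeutic and motivational use in burned children.

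The Statistical Analysis Plan specifies a 2×2 mixed-design MANOVA (group by time) and states: "The variable of interest was the group-by- time interaction". It includes no term for therapy time.

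**The concern.** The word *alternative* in the Background can be read as *instead of*. On that reading the trial would be testing whether Xbox can take the place of conventional exercise. The Methods describe something else: the same routine care in both arms, with extra sessions in one. The aim names only an Xbox intervention, and the Conclusion credits that intervention with the benefit. Neither repeats that it was an addition.

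The stake is interpretation. If the interaction is significant, the data support the statement that adding these sessions to routine therapy helped. They do not show that Xbox can substitute for other exercise, or that the gaming element does more than the same number of extra minutes of any exercise would do. A clinician who read only the aim and the Conclusion might draw one of those stronger inferences.

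**Working it through.** **Inputs.** From the Methods: 50 minutes per Xbox day, 3 days a week, 12 weeks; routine therapy for 12 weeks in both arms; 20 children per arm. From the Statistical Analysis Plan: the effect of interest is the group-by-time interaction. Not given anywhere: the weekly minutes of the routine programme (call this R), attendance, and whether the Xbox sessions were supervised.

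**Figures in the plan to reproduce.** There is no total of added hours and no sample-size derivation. The arm sizes agree with the total: 20 + 20 = 40.

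**Prescribed addition.**
- Sessions: 3 × 12 = 36.
- Weekly time: 50 × 3 = 150 min.
- Total: 150 × 12 = 1,800 min = 30 h per child.

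This takes 50 minutes as the whole five-game session. Reading it as 50 minutes per game would give 5 × 30 = 150 h, which is implausible. The 30 h is a maximum. At an assumed 70% attendance it would be 0.70 × 30 = 21 h.

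**Relative session time.** If R is equal in both arms, the ratio of prescribed time, Xbox arm to control arm, is (R + 150)/R. All values of R below are assumed.

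| R (min/week) | Calculation | Ratio |
|---|---|---|
| 60 | 210/60 | 3.5 |
| 150 | 300/150 | 2.0 |
| 300 | 450/300 | 1.5 |
| 600 | 750/600 | 1.25 |
| 900 | 1,050/900 | 1.17 |

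The ratio exceeds 1 for any R, but its size depends wholly on the value chosen. It also measures minutes prescribed, not bias in an outcome.

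**Can the analysis separate mode from time?** Prescribed extra time is 30 h for every child in the Xbox arm, and no extra sessions are described for any control child. Extra time is therefore 30 × (arm indicator). A model containing both terms cannot be identified, so no covariate adjustment or reanalysis of these two arms would help.

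**What each part of the document asserts.**

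| Place | States the add-on? | Claims substitution or superiority to time-matched exercise? |
|---|---|---|
| Background and aim | No; *alternative* is ambiguous | No |
| Methods | Yes, explicitly | No |
| Conclusion | No | No |
| Statistical Analysis Plan | Compares the two arms as defined in the Methods | No |

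Read together, the four parts define one contrast without contradiction: routine therapy plus the Xbox programme against routine therapy. That contrast answers an aim of exploring the outcomes of an Xbox intervention, since an intervention includes its sessions.

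**The case for a change.** The best argument for a change is that aims and conclusions are what people carry away. The Conclusion speaks of virtual reality as a motivational tool, which points towards the gaming mode as the active ingredient. The Background's adjective invites a substitution reading. A few added words would close both routes at almost no cost. Because mode and added time coincide completely, careful wording is the only remedy available within this design.

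Part of this stands. It is true that the aim and the Conclusion omit the qualifier, and true that these two arms cannot isolate the mode.

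The rest is weaker. *Alternative* may simply mean a different kind of exercise, which fits the Methods. The stronger inferences are ones a reader would have to supply, because the document makes neither. To miss the add-on contrast, that reader would have to skip the few sentences that lie between the aim and the Conclusion. Extra staff contact is sometimes raised alongside extra time as an explanation, but supervision and setting are not described, so contact would be an inference and not a fact of the plan.

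**Conclusion.** No change is needed. The Methods prescribe up to 30 h of Xbox sessions on top of routine therapy in one arm only, so the estimated effect is that of the added package and cannot be attributed to Xbox as a mode. This is an ordinary feature of an add-on trial against usual care. It becomes a defect only if the trial claims to answer the mode or substitution question, and it does not.

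The omission from the aim and the Conclusion is missing detail that any reader or analyst fills correctly from the Methods. Repeating it would alter no allocation, outcome, model or result, and the Conclusion is sound when read with the Methods. Whether to repeat it is an editorial choice.

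This rests on two readings: that 50 minutes is the full daily session, and that the routine programme is the same in both arms. The 30 h assumes full attendance. The ratios of session time are illustrative only, because R is not stated.

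### Age and burn size enter neither the treatment comparison nor any described stratification, so their effect on 12-week change goes unadjusted; fixed adjustment would be a cheap gain in precision and protection against chance imbalance

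*Combined protocol and SAP*

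**What the plan says.** The Methods paragraph of the Study Protocol describes the sample as "Forty burned children with burns covering 40–60% of the total body surface area (TBSA), aged 10–16 years", who "were randomized into the standard of care (n=20), and Xbox training group (n=20) groups". It describes no stratification or minimisation.

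The Statistical Analysis Plan handles baseline balance in one sentence: "Potential differences in baseline demographic between groups were examined using independent sample t-tests". It does not list the variables that count as demographic, so a reader cannot tell whether TBSA was among them. It gives no significance level for these tests and no consequence of a significant or non-significant result.

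Treatment is tested by a 2x2 mixed-design MANOVA on five dependent variables, "within group as the between-subject variable (experimental received and control received") and "time as the within-subject variable (pre and post treatment"). The term of interest is fixed as follows: "The variable of interest was the group-by- time interaction at an a priori alpha level of 0.05 and 95 % confidence interval". Neither age nor TBSA appears as a covariate or factor.

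**The concern.** The entry range is wide for a trial of 40 children. Twelve-week change in lean mass, leg torque and peak VO₂ could plausibly depend on age, through growth, and on burn size, through recovery. Eligibility cannot be checked without both variables, so it is a safe inference, though not a statement in the text, that both are known for every child.

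A significance test of baseline balance does not help here. Under proper randomisation any baseline difference is due to chance, so the test answers a question that is already settled. What matters is the size of the imbalance multiplied by how strongly the variable predicts change, and a t-test does not measure that. With 20 per arm, a non-significant result could be taken as evidence of comparability while a moderate gap stays in the group contrast. If age or TBSA does predict change, leaving it out of the model also leaves explainable variance in the error term.

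**Working it through.** The documents give no age SD, effect size or sample-size rationale, so there is no figure of the plan's own to reproduce.

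**Inputs from the documents:** 20 per arm; age 10–16; TBSA 40–60%; alpha 0.05 for the interaction. **Assumed:** ages uniform over the range; two-sided 0.05 for the baseline t-tests; correlation r of age with 12-week change of 0.3 or 0.5.

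**1. What the interaction removes.** For one outcome, write pre = a + b·age and post = a + b·age + δ·group + c·age. The change is δ·group + c·age. The level term b·age cancels. The group contrast in change is δ + c·(age gap between arms), so only the effect of age on change remains. The same holds for TBSA.

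**2. What the t-test flags.** SD = 6/√12 = 1.73 years. SE of the difference in means = 1.73 × √(2/20) = 0.548. The smallest observed gap reaching p < 0.05 is t(0.975, 38) × 0.548 = 2.024 × 0.548 = 1.11 years. For TBSA on the same assumption, SD = 20/√12 = 5.77 points and the threshold is 3.70 points.

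**3. How often chance leaves an unflagged gap.** P(gap ≥ 0.75 year) = 2 × [1 − Φ(0.75/0.548)] = 17%; P(gap ≥ 1 year) = 2 × [1 − Φ(1/0.548)] = 7%. In a simulation of 400,000 randomisations with uniform ages, the gap is present and the t-test is non-significant in:
- about 12% of randomisations for a gap of at least 0.75 year;
- about 2% for a gap of at least 1 year (the test flags about 72% of gaps this large).

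**4. Size of the shift.** In SD of change, the shift is r × gap / SD of age.

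| Gap | r = 0.3 | r = 0.5 |
|---|---|---|
| 0.75 year | 0.13 | 0.22 |
| 1 year | 0.17 | 0.29 |

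**5. Error rate given a 1-year gap.** Let k = shift/√(2/20). The unadjusted test uses the total SD, while the contrast given the gap has SD smaller by the factor √(1 − r²). The two-sided error is therefore Φ[−(1.96 − k)/√(1 − r²)] + Φ[−(1.96 + k)/√(1 − r²)].
- r = 0.3: k = 0.548, error 0.074, about 7%.
- r = 0.5: k = 0.913, error 0.114, about 11%.

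Averaged over all randomisations the error stays at 5%.

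**6. Gain and cost of adjusting for both variables.** The variance ratio, adjusted to unadjusted, is about (1 − R²) × (1 + 2/35), where R² is the share of variance in change explained jointly by age and TBSA.

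| R² | Ratio | Variance |
|---|---|---|
| 0 | 1.057 | 6% more |
| 0.054 | 1.000 | break-even |
| 0.1 | 0.951 | 5% less |
| 0.2 | 0.846 | 15% less |
| 0.3 | 0.740 | 26% less |

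**The case against.** The strongest reply is that a randomised comparison needs no covariates to be valid, that the pre/post design already deals with most of what age and burn size do to these outcomes, and that the benefit rests on correlations the documents do not supply. Most of this stands. The interaction does remove level differences, and the 5% error rate does hold over randomisations. The gain could be nil: below a joint R² of about 5%, adjustment costs slightly more than it returns. The gain would also shrink if each outcome's own baseline value were used as a covariate, because age and baseline overlap.

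Two stronger readings are tempting. A reader might infer that the t-test would miss a one-year age gap more often than not. Power for a true one-year difference is 43% at SD 1.73, but the documents give no SD, and the statement reverses below about 1.57 years (46% missed at SD 1.5, 31% at 1.25). A true difference is also the wrong quantity: randomisation produces only chance gaps, and an unflagged one of a year or more is uncommon. A reader might also infer that the baseline t-tests are the plan's only answer to the spread in age and burn size. The group-by-time term shows otherwise.

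It is also fair to object that the text is written in the past tense and carries a conclusion, so covariates added now might not be pre-specified. That limits how the result may be labelled. It does not remove the value of showing it.

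What survives is narrow: no part of the plan addresses an effect of age or TBSA on change, and the t-tests do not fill that gap.

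**Conclusion.** The point holds as a modest improvement in precision and in protection against chance imbalance. It is not an error that invalidates the comparison. The omission of age and TBSA from the model, and the absence of any described stratification, can be read directly from the text.

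The size rests on assumptions. The 12% and 2% figures need ages spread evenly over the entry range; a tighter spread makes such gaps rarer. The shifts, and the 7% and 11% error rates, need an assumed correlation with change and apply only given a 1-year gap. All figures are for one outcome at a time. For TBSA the documents support no more than the 3.70-point threshold under the same uniform assumption. The recommendation depends little on any of these numbers, because the cost is bounded at about 6% of variance.

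**What to change.** Replace the baseline t-tests with a table of baseline characteristics by arm, including age and % TBSA, without p-values. In the treatment comparison for each outcome, include age and % TBSA as continuous covariates, so that their effect on the 12-week change is modelled. Keep them whatever the observed balance, and report the unadjusted comparison alongside.

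If the analysis has already been run, report the adjusted result as a sensitivity analysis and do not describe it as pre-specified.

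The cost is a few sentences in the Statistical Analysis Plan, a few lines of analysis on data needed for eligibility, and two of the 38 error degrees of freedom.

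### The only efficacy test is one joint test of unadjusted change in five variables; baseline-adjusted estimates with confidence intervals should be added for each outcome

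*Combined protocol and SAP*

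**What the plan says.** The Methods paragraph of the Study Protocol states that 40 children "were randomized into the standard of care (n=20), and Xbox training group (n=20) groups", with outcomes taken at baseline and at 12 weeks. The Background paragraph gives the aim: "To explore the outcomes of an Xbox Kinect intervention on muscle strength, lean body mass (LBM) and cardiopulmonary fitness". The Conclusion paragraph then claims improvement in all three of these domains.

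The Statistical Analysis Plan has one efficacy model: "2x2 mixed design MANOVA was used to examine the effect of" "treatment on the measured dependent variables (LBM, trunk, leg, Vo2 and PT"), with time (pre and post) as the within-child factor. The decision rule is: "The variable of interest was the group-by- time interaction at an a priori alpha level of 0.05". That sentence goes on to mention a 95% confidence interval but does not say for which outcome or contrast. The only other between-group test is on baseline characteristics: "Potential differences in baseline demographic between groups were examined using independent sample t-tests".

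The plan names no primary outcome, baseline-adjusted model, follow-up test for single outcomes or multiplicity rule.

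**The concern.** There are two gaps, and neither depends on missing data or protocol deviations.

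- **Unused baseline.** Each outcome is measured before treatment, but the interaction uses that value only by subtraction. With 20 children per arm, a chance difference in baseline strength, VO2 or lean mass carries into the estimated effect, and precision is lost unless pre and post values are very highly correlated. T-tests on demographics correct nothing and do not look at the outcome baselines.
- **No answer for any one outcome.** Rejecting the joint hypothesis shows only that the arms differ somewhere among five variables. The protocol wants to speak about strength, lean mass and fitness separately, and the planned test cannot support three separate statements.

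**Working it through.** **Inputs.** From the documents: 20 per arm, two visits, five variables, alpha 0.05. Assumed, because the documents give none: pre/post correlation ρ, between-outcome correlation r, and effect size. The plan gives no sample-size calculation, so it has no figure of its own to reproduce.

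**1. What the interaction tests.** With two visits, the interaction contrast for each variable is (post − pre) in the Xbox arm minus (post − pre) in the control arm. Across five variables, the test is Hotelling's T² on five change scores, referred to F with 5 and 40 − 5 − 1 = 34 degrees of freedom.

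**2. Precision for one outcome.** With equal pre and post SDs, in units of outcome variance, the change score has variance 2(1 − ρ) and ANCOVA has 1 − ρ². The ratio is (1 + ρ)/2. Estimating the slope at N = 40 multiplies this by about 1 + 1/36.

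| ρ | (1 + ρ)/2 | with slope cost | SE ratio |
|---|---|---|---|
| 0.3 | 0.65 | 0.67 | 0.82 |
| 0.5 | 0.75 | 0.77 | 0.88 |
| 0.7 | 0.85 | 0.87 | 0.93 |
| 0.9 | 0.95 | 0.98 | 0.99 |
| 0.95 | 0.975 | 1.00 | 1.00 |

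Simulation at ρ = 0.7 gave 0.872. With unequal SDs, var(change) − var(ANCOVA) = (SD_pre − ρ·SD_post)², which is never negative, so adjustment can lose only the slope cost of about 3%.

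**3. Chance imbalance.** One standard error of the baseline difference is √(2/20) = 0.32 SD. The change-score estimate shifts by (1 − ρ) × 0.32 SD, which is 0.22, 0.16, 0.09, 0.03 and 0.02 SD at the five values of ρ. ANCOVA removes this shift. Over all randomisations, both tests hold about 5% false positives (4.8 to 5.1% simulated).

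**4. Multiplicity of five ANCOVAs.** Unadjusted at 0.05, the family-wise error is 1 − 0.95⁵ = 22.6% if the outcomes are independent, and about 15.5% at r = 0.7 (simulated). Holm brings it to 3.6–4.9%. Holm's first step is 0.05/5 = 0.01. For an effect of 0.8 SD of change at ρ = 0.5, this cuts the power of a single ANCOVA from 80% to 57%.

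**5. Holm-ANCOVA against the planned joint test.** Chance of at least one rejection, with an effect of 0.8 SD of change and ρ = 0.5:

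| Pattern | r | Holm-ANCOVA | Joint MANOVA |
|---|---|---|---|
| all five move | 0.3 | 94% | 78% |
| all five move | 0.5 | 89% | 63% |
| all five move | 0.7 | 83% | 51% |
| one moves | 0.3 | 58% | 48% |
| one moves | 0.5 | 59% | 63% |
| one moves | 0.7 | 59% | 86% |

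At ρ = 0.9 with one outcome moving, Holm-ANCOVA gives 46–47% against the same MANOVA figures, so the MANOVA is level or ahead throughout.

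**The case against.** The MANOVA is a valid test of any effect, and the baseline point concerns efficiency, not validity. That is correct. The efficiency gain depends on a correlation that the documents do not give. Lean mass at ages 10–16 may have a very high pre/post correlation; if the trunk and leg variables are also lean-mass measures, three of the five outcomes might gain almost nothing. That also stands.

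The plan mentions a 95% interval, and a joint F test does not yield a single one, so intervals for individual variables were perhaps intended. This softens the second gap but does not close it, because no contrast or outcome is attached to the interval.

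A reader might infer three stronger points that the documents do not support:

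- **ANCOVA is simply the better test.** A comparison of two single-outcome tests at 0.05 (69% for change against 80% for ANCOVA at ρ = 0.5) suggests this, but it is not the comparison with the plan's joint test. That comparison, in step 5, goes either way.
- **Children are lost through incomplete data.** A standard MANOVA drops a child with any missing value. If each of three tests were missed independently in 5% of children, 1 − 0.95³ = 14.3% would be lost; with five separate values, 1 − 0.95⁵ = 22.6%. But no missing value is reported, and the loss is zero with complete data.
- **The analysis is as-treated.** The factor is worded "group as the between-subject variable (experimental received and control received"). The Methods paragraph uses the same verb for care given to the randomised arms ("All burned children received 12 weeks of routine physical therapy program"), and no crossover is reported. It is most naturally an arm label.

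**Conclusion.** The point holds as an inexpensive improvement, not as a demonstration of bias. The planned test controls its error rate, but it does not adjust for the measured baselines and cannot attribute an effect to strength, lean mass or fitness.

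The benefit of adjustment for each outcome ranges from an interval about 18% narrower at ρ = 0.3, through 12% at 0.5 and 7% at 0.7, to 1% at 0.9 and nothing at 0.95. All of these rest on assumed correlations. The gain in interpretability does not depend on them.

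The Conclusion paragraph already speaks of findings, so a primary outcome named now would be post hoc. Unless one was documented before results were seen, Holm across the five variables is the applicable rule.

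**What to change.** In the Statistical Analysis Plan:

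1. For each of the five variables, add an ANCOVA of the 12-week value on its own baseline and randomised group, using every child with data for that variable. Report the adjusted difference with its 95% interval.
2. Apply Holm across the five, unless a primary outcome was documented before results were seen. In that case test it at 0.05 and treat the other four as secondary.
3. If results are already known, label the added analyses post hoc.
4. Keep the MANOVA as the global test.

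The cost is a few sentences and a re-run on data already collected. Each ANCOVA uses one degree of freedom and assumes a linear baseline slope. Holm costs power for any single outcome. Keeping the MANOVA covers the pattern in which Holm-ANCOVA is weaker (about 59% against 86% when one outcome moves, r = 0.7 and ρ = 0.5).

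### Optional precision gain: the pre/post interaction compares raw change for each outcome, and ANCOVA on the outcome's own baseline is usually more precise in expectation

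*Combined protocol and SAP*

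**What the plan says.** The Methods paragraph of the Study Protocol says that children "were randomized into the standard of care (n=20), and Xbox training group (n=20) groups", and that "Outcomes were measured at baseline and after 12 weeks of intervention". There are therefore 40 children, equal arms and two measurements of each outcome.

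The Statistical Analysis Plan states that a "2x2 mixed design MANOVA was used to examine the effect of" "treatment on the measured dependent variables (LBM, trunk, leg, Vo2 and PT"), with group between subjects and "time as the within-subject variable (pre and post treatment"). The effect of interest is the group-by-time interaction, at "an a priori alpha level of 0.05 and 95 % confidence interval". Baseline values of the outcomes enter only as the first level of time, and no other baseline adjustment is mentioned. No follow-up analysis outcome by outcome is described. The documents state no pre-post correlation, SD, effect size or power.

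**The concern.** When time has only two levels, the interaction for one outcome is the difference between arms in mean post-minus-pre change. Subtracting the baseline amounts to fixing the slope of the 12-week value on baseline at 1. If the true slope differs from 1, some baseline variation stays in the comparison as noise. ANCOVA estimates the slope and removes that noise, at the price of one degree of freedom.

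What is at stake is precision only. Under randomisation the change-score comparison is unbiased and its test is valid. The question is whether a trial of 40 children leaves unused some per-outcome precision that its own data could supply.

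**Working it through.** **Inputs.** From the documents: 20 children per arm, two measurement times, five outcomes, alpha 0.05. Assumed, because the documents give no values: pre-post correlation r of 0.5, 0.7 and 0.9; post/pre SD ratio s from 0.8 to 1.25; normal baselines; a common slope in both arms; no dropout. There is no figure in the plan to reproduce.

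**Formulae.** Set the baseline SD to 1, so the post SD is s and the true slope is b = rs.

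- Residual variance: V = s²(1 − r²).
- Change-score variance: s² + 1 − 2rs = V + (1 − b)².
- ANCOVA variance: V × (1 + 1/36) = V × 37/36. The 1/36 is the expected cost of estimating one slope with N = 40, because 1/(N − 4) = 1/36.
- Ratio, ANCOVA to change: (37/36) × V / [V + (1 − b)²].

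Since (1 − b)² cannot be negative, the expected ratio never exceeds 37/36 = 1.028.

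**Equal SDs (s = 1).** The ratio simplifies to (37/36) × (1 + r)/2.

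- r = 0.5: 1.0278 × 0.75 = 0.771, or 23% lower.
- r = 0.7: 1.0278 × 0.85 = 0.874, or 13% lower.
- r = 0.9: 1.0278 × 0.95 = 0.976, or 2% lower.
- Break-even: r = 72/37 − 1 = 0.946.

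Simulation agreed, with ratios of 0.769, 0.876 and 0.977. In equivalent children per arm, 20 divided by the ratio gives 25.9, 22.9 and 20.5. The 95% CI is 12%, 6% and 1% narrower. If the effect were such that the change-score test of one outcome had 80% power, ANCOVA would have 89%, 85% and 81%.

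**Other SD ratios.** Change in expected variance from using ANCOVA:

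| Post/pre SD ratio | r = 0.5 | r = 0.7 | r = 0.9 |
|---|---|---|---|
| 0.8 | −41% | −35% | −38% |
| 0.9 | −31% | −23% | −17% |
| 1.0 | −23% | −13% | −2% |
| 1.1 | −16% | −5% | +3% |
| 1.25 | −8% | +1% | −2% |

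As an example, at s = 1.1 and r = 0.9, V = 1.21 × 0.19 = 0.2299. The ANCOVA variance is 0.2299 × 37/36 = 0.2363, the change variance is 1.21 + 1 − 1.98 = 0.23, and the ratio is 1.027. An expected loss occurs for r above 0.946 at s = 1.0, between 0.81 and 0.96 at s = 1.1, and between 0.68 and 0.88 at s = 1.25. There is none at 0.8 or 0.9.

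**A single trial.** The 2.8% is an average over chance baseline imbalance. If the true slope is 1, the variance inflation in one 20-versus-20 trial is t²/38, where t is that trial's baseline t statistic. It exceeds 1/36 when |t| > √(38/36) = 1.03, which happens in about 31% of trials. At |t| = 2.024, which is exceeded in 5% of trials, it is 4.098/38 = 10.8%.

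**The case against.** The strongest reply is that the plan's stated test is multivariate, and nothing here faults it. That stands. Single-outcome change-score estimates are not spelled out. They are inferred from the call for a 95% confidence interval, because a joint test on five outcomes does not itself yield an interval for a treatment effect. The inference is reasonable, but the gain matters only if outcomes are also reported singly.

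Second, the gain may be small where it is most wanted. The Methods say "lean body mass was determined using dual-energy X-ray absorptiometry", a measure that probably tracks strongly from baseline to 12 weeks. The undefined trunk and leg variables would do the same if they are regional lean mass. At r near 0.9 the result runs from a useful gain to a slight loss. This also stands, and it is why the 23% must not be read as the expected benefit across the trial.

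Third, the analysis seems to have been done already: "Reported data was analyzed using Statistical Package for Social Sciences (SPSS) computer program". Extra unplanned estimates then give some room for selective reporting. Reporting all five, labelled as such, answers most of that.

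A reader might also infer that the joint test should become a MANCOVA on all five baselines, or that such a MANCOVA is known to be worse. The documents support neither. Where MANOVA on changes has 80% power, equal SDs and cross pre-post correlations equal to r times the within-time correlations give MANCOVA power of 85%, 80% and 74% at r = 0.5, 0.7 and 0.9. Under other correlation structures the figure at r = 0.7 ranged from about 74% to 95%. The answer turns on r, the SD ratio and between-outcome correlations, none of which is given.

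**Conclusion.** The point holds as an optional efficiency improvement. Outcome by outcome, the planned interaction is a valid comparison of raw change, and in expectation it is usually less precise than own-baseline ANCOVA.

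The size rests wholly on assumed r and SD ratios. It is a worthwhile gain at moderate r with a stable or shrinking SD, and close to nothing at high r with a stable or slightly growing SD.

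Two stronger readings should be resisted. One is that the planned test is biased or wrong; randomisation makes it valid. The other is that ANCOVA can never cost more than 2.8%; that bound is on the expected variance with normal baselines, and one trial with marked imbalance can exceed it.

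**What to change.** Keep the planned MANOVA group-by-time interaction as the joint test. For each of the five outcomes, add a regression of the 12-week value on randomised group with that outcome's own baseline as the only covariate. Report the adjusted difference with its 95% CI. If these differences are tested, apply Holm across the five. Make no general statement for or against a five-baseline MANCOVA.

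If the analysis has not been run, this costs a few lines of SAP text and one degree of freedom per outcome (37 instead of 38), with the same data and software. If it has been run, report the five estimates, all of them, beside the planned test and label them as non-prespecified. The downside is the small expected loss for any outcome whose true slope on baseline is close to 1.
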